### 1.1 Primary:

1. Estimate the proportion of patients with metastatic RCC treated with IL-2 combined with hydroxychloroquine at 600 mg/d who experience a clinical complete response.

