### **2.18 Early experience with the regimen.**

The first five patients were treated with 600mg of Hydroxychloroquine with one patient deemed a complete response. Out of the 13 patients treated with combination HCQ/IL-2 therapy using 1200 mg of Hydroxychloroquine, two patients experienced pronounced hypotension and tachycardia. Furthermore, one patient died from pulmonary emboli, not attributed to therapy. The cardiac events are consistent with IL-2 toxicities, but were observed somewhat earlier in the course of treatment. For that reason we are accruing another 21 patients to assess response in addition to the first five patients at the lower 600mg/d dose.

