## 13.0 STATISTICAL ANALYSIS AND STUDY SIZE

### 13.1 Objectives and Design

The primary objective of this Phase II trial is to estimate the proportions of patients with metastatic RCC treated with high-dose IL-2 combined with hydroxychloroquine experiencing complete response, or any response. The secondary objectives are to compare response, time to progression and survival to historical data to determine the toxicity of the treatment regimen, to evaluate PD, and to examine correlative science endpoints. Disease endpoints are defined in Section 10.

The accrual goal is 39 participants. All study participants will receive the same high-dose IL-2 treatment, which is considered standard of care. The initial dose of HCQ will be 600 mg/day for all patients. If no limitations on additional dosing (treatment-limiting toxicities [TLTs], as defined in Section 9.2), dosing will continue at 600mg/d, otherwise, HCQ will de-escalate to 400 mg/d. Toxicity and response will be monitored after every three patients (Section 13.4), and will be stopped if the probability that treatment with IL-2+HCQ is excessively toxic or ineffective. The study may be opened more broadly to additional Cytokine Working Group sites whenever sufficient evidence has accrued that treatment with IL-2+HCQ is no more toxic or less effective than treatment with IL-2 alone.

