### **13.3 Monitoring for Toxicity and Response**

**13.3.1** 21 additional patients will be enrolled at IL-2+HCQ 600 mg/day on this revised protocol. If one or more TLTs are observed, treatment will be de-escalated to IL-2+HCQ 400 mg/day.

**13.3.2** The number of overall partial and complete responses (**Table 8**) will be compared to the stopping rule described in Table 10 by the UPCI Multi-Center DSMC after every three patients become evaluable for response. For each number of evaluable patients in the left-hand columns, if the number of complete responses is less than or equal to the number in the right-hand column, the trial will be halted for lack of efficacy. The trial is derived from a Bayesian beta-binomial model with the prior determined by the number of complete responses observed in the high-dose arm of the randomized trial described in Section 2.3 (8/95). The values correspond to P (partial and complete response rate < 0.10) > 0.8.

# Patients	#Responses
18	0
21	1
24	1
27	1
30	2
33	2
36	2

*Table 8.* Monitoring rule for complete response. For the given number of patients in Column 1, if the number of partial or complete responses is less than or equal to the number in Column 2, the trial is halted for lack of efficacy.

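### Table 8 does not say which dose group it counts, and its rows from 27 to 36 cannot be reached with the 26 patients planned at 600 mg/d

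*Combined protocol and SAP*

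**What the plan says.** Section 1.1 sets the primary objective as the proportion of patients on IL-2 "combined with hydroxychloroquine at 600 mg/d who experience a clinical complete response".

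Section 2.18 reports what has already happened: "The first five patients were treated with 600mg of Hydroxychloroquine with one patient deemed a complete response". It then describes events "Out of the 13 patients treated with combination HCQ/IL-2 therapy using 1200 mg of Hydroxychloroquine", without giving the number of responses at that dose. It adds that "we are accruing another 21 patients to assess response in addition to the first five patients at the lower 600mg/d dose". Section 13.3.1 repeats the number: "21 additional patients will be enrolled at IL-2+HCQ 600 mg/day on this revised protocol". The Summary and Schema also gives a group of 21 at 600 mg/d.

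Section 13.1 says: "The accrual goal is 39 participants", and also: "The initial dose of HCQ will be 600 mg/day for all patients". Section 13.4 treats 39 as the number available for the 600 mg/d objective.

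Section 13.3.2 has the monitoring committee compare responses with the table "after every three patients become evaluable for response". The trial halts if responses are at or below 0, 1, 1, 1, 2, 2, 2 at 18, 21, 24, 27, 30, 33, 36 evaluable patients. No dose restriction is given. The same section words the response count both as complete responses and as partial plus complete responses.

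**The concern.** This is the plan's only numerical rule for stopping for lack of efficacy, and it is worded as an instruction to halt. A committee holding the data needs to know whose responses to count. Counting 600 mg/d patients only, four of the seven rows can never be used. Counting everyone treated, the table fits the total, but results at a dose the trial has left then enter the verdict on the dose under study. Two committees with identical 600 mg/d data could reach opposite decisions. One error would halt a regimen that meets its target. The other would leave no protection against an inactive one.

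**Working it through.** **Patient counts**
- At 600 mg/d: 5 already treated (2.18) + 21 further (2.18, 13.3.1) = 26.
- Already treated at either dose: 5 + 13 = 18.
- Overall: 18 + 21 = 39, the accrual goal in 13.1.
- Table 8 rows reachable with 26 patients: 18, 21, 24. Not reachable: 27, 30, 33, 36.
- If all 39 were at 600 mg/d, as 13.1 and 13.4 read literally, 39 − 5 = 34 further patients would be needed there. The plan gives 21.

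**Reproducing Table 8**

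Take the prior 8/95 as Beta(8, 87). With x responses in n patients the posterior is Beta(8 + x, 87 + n − x). The boundary at n is the largest x with P(rate < 0.10) > 0.8. This gives 0, 1, 1, 1, 2, 2, 2 at n = 18 to 36, matching all seven rows. The same model also gives a boundary of 0 at n = 9, 12 and 15, so it does not force a first row at 18.

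**Stopping probabilities**

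Assumptions: complete responses are counted, all treated patients are evaluable, and there is 1 response in the first 5. Let p be the true rate in new 600 mg/d patients.

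*600 mg/d only, from 1/5.* Row 18 (boundary 0) cannot fire. Row 21 fires only if the next 16 patients have no response, and row 24 then adds nothing. P(stop) = (1 − p)^16.

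*Both doses counted:*
- 0 of 13 responded, start 1/18. Stop at 21 if the next 3 have no response. Otherwise stop at 30 if those 3 gave exactly one response and the following 9 none. P(stop) = (1 − p)^3 + 3p(1 − p)^11.
- 1 of 13 responded, start 2/18. Stop at 30 if the next 12 have no response. P(stop) = (1 − p)^12.
- 2 or more of 13 responded. The total is at least 3, above every boundary, so P(stop) = 0 whatever p is.

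| True rate p | From 1/18 | From 2/18 | From 3/18 or more | 600 mg/d only |
|---|---|---|---|---|
| 4% | 96% | 61% | 0% | 52% |
| 8.4% (8/95) | 86% | 35% | 0% | 25% |
| 16% (twice 8%, 13.4) | 66% | 12% | 0% | 6% |

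At 16% the 66% is 0.84^3 + 3 × 0.16 × 0.84^11 = 0.593 + 0.071. The first term is a halt at row 21 with only 5 + 3 = 8 patients treated at 600 mg/d.

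**Averaging over the unknown result at 1200 mg/d**

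Suppose both doses share the rate p.
- At 16%: P(0/13) = 0.84^13 = 0.104 and P(1/13) = 13 × 0.16 × 0.84^12 = 0.257. The average is 0.104 × 0.663 + 0.257 × 0.123 = 0.10.
- At 4%: P(0/13) = 0.588 and P(1/13) = 0.319. The average is 0.588 × 0.961 + 0.319 × 0.613 = 0.76.

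**If partial responses also count**

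The starting counts are then unknown, because 2.18 reports no partial responses. For illustration at p = 25%, the independently reviewed overall response rate quoted in 2.2: 45% from 1/18, 3% from 2/18, and 1% on a 600 mg/d count from 1/5.

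**The case against.** The strongest reply is that no section says the two doses are pooled. A reader might infer from the matching totals that the 1200 mg/d patients are counted, but that remains an inference. Sections 13.1 and 13.4 can be read as placing all 39 at 600 mg/d, and the table might also have been carried over from another stage of the design. This stands. The literal reading nevertheless contradicts the 21 further patients given in three places, so under any reading some passage must change.

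The match between the first row and 5 + 13 is also weak evidence. Table 8 counts evaluable patients, section 2.18 counts treated ones, and section 11.0 requires eligibility and at least a week of IL-2. Nor does the inert first row point to pooling: with one response already recorded, it is equally inert on a 600 mg/d count.

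A reader might further infer that the rule must either halt a good regimen or never stop at all. The figures do not support that. From 2/18 the stopping probability at 16% is 12%, and from 1/18 or 2/18 the new 600 mg/d outcomes still decide. The 66% needs 0 of 13 at 1200 mg/d, which has probability 10% if that dose also has a 16% rate; it is more likely if the rate there is lower.

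Finally, the primary aim is estimation, and one clarifying sentence would remove much of the ambiguity. That limits the repair needed, but 13.3.2 still orders a halt.

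**Conclusion.** The concern holds as an undefined monitoring set and an unreconciled sample size. The unreachable rows follow directly from 26 planned patients at 600 mg/d and need no assumption about pooling.

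The effect of pooling is conditional. It requires that the 1200 mg/d patients are in fact counted, and the figures assume a complete-response count, full evaluability, and one response in the first five. On those terms the decision at 600 mg/d is sensitive to the other dose in both directions. With no response among the 13, stopping at a true 16% rises from 6% to 66%. With two or more, even 0 of 21 new responses at 600 mg/d could not stop the trial, although a 600 mg/d count of 1/21 would. The average effect is much smaller, about 10% against 6% at a shared 16% rate. The documents do not give the number of responses at 1200 mg/d, so they cannot show which case applies.

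**What to change.** Before the next look:
1. Reconcile the 39 in 13.1 and 13.4 with the 26 at 600 mg/d, and correct the statement about the starting dose of all patients so that it agrees with 2.18.
2. State in 13.3.2 that only evaluable patients who started at 600 mg/d count toward Table 8.
3. Name one response endpoint for the rule. If it is partial plus complete response, report that count for the first five patients and revisit the prior, which is built from complete responses.
4. Re-issue the table on a grid ending at 24 and print its stopping probabilities for the chosen endpoint. For complete response, show at least 4%, 8% and 16%.

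This takes one recomputed table and a few sentences, with no extra patients. There is a real cost: fewer looks and less power to stop an ineffective regimen. At a true 4%, the existing rows up to 24 stop with probability 52% on a 600 mg/d count, against about 76% with both doses counted if they share that rate. The re-issued table should show this loss so that the sponsor can judge whether it is acceptable.

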### 13.4 Justification of Design

The primary objective of this study is to estimate the clinical response rate of patients with metastatic RCC treated with IL-2 combined with hydroxychloroquine at 600mg/d. Assuming no TLTs occur and the trial is not closed early for toxicity or inadequate response (Section 13.3.2), there will be 39 patients available for this objective. A 95% exact binomial confidence interval on 5 responses out of 39 patients (expected if the addition of HCQ to IL-2 doubles the historic proportions of CR ~ 8%) would have width equal to 0.27 (0.07,0.34). For the secondary endpoints of OS and PFS, if patients are recruited over 15 months, observed for 15 additional months, and the true median survival is 16 months, then the expected width of the 95% confidence interval for median survival is 12.8 months.

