### 13.2 Analysis Plan

The data will be analyzed for response, overall survival and other endpoints, as described in this section; data will only be analyzed as specified in Section 14.3.1 to ensure the toxicity of IL-2+HCQ is not unexpectedly high. All analyses will be performed using the most recent versions of SAS and/or R available.

- 13.2.1.** *Estimate the proportion of patients with metastatic RCC treated with IL-2 combined with hydroxychloroquine at 600mg/d who experience a clinical complete response.* Response is defined in Section 10.3. The probability of each category of response will be estimated. Secondary analyses will employ cumulative logit regression for increasing levels of response, with adjustment for demographic and clinical covariates. All point estimates will be accompanied by appropriate 95% confidence intervals.
- 13.2.2.** *Compare the response, overall survival and time to progression of patients with metastatic RCC treated with IL-2 combined with hydroxychloroquine to the published response of patients treated with high dose IL-2 alone.* Logistic and proportional hazards (Cox) regression will be used to compare clinical response, and OS and PFS, respectively, to examine the effect of HCQ on the efficacy of IL-2. Formal tests of non-inferiority are beyond the scope of this Phase II study, and these secondary analyses are not statistically powered.
- 13.2.3.** *Characterize the toxicity of IL-2 combined with hydroxychloroquine in patients with metastatic RCC: number of doses of IL-2 administered during the first course of therapy; toxicity after the scheduled 9th dose of IL-2; frequency of grade III and IV or unexpected or rare toxicities.* Number of doses, maximal toxicity grade and incidence of treatment-limiting toxicities (TLTs, as defined in Section 10.5) will be tabulated.

**13.2.4** *Evaluate the utility of known prognostic criteria for RCC patients on clinical outcome.* Prognosis is evaluated by whether the patient has 0, 1, or 2, or 3 or more of the following risk factors:

- lactate dehydrogenase (> 1.5 upper limit of normal)
- hemoglobin (< lower limit of normal)
- corrected calcium (>10mg/dL)
- Karnofsky performance status (< 80%)
- time from initial RCC diagnosis to start of interferon- $\alpha$  therapy of less than one year

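### Section 13.4 rests the 600 mg/d primary estimate on 39 patients where Section 2.18 implies 26, and the exact interval it prints is wrong for its own 5/39

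*Combined protocol and SAP*

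**What the plan says.** The primary objective in Section 1.1 concerns patients "treated with IL-2 combined with hydroxychloroquine at 600 mg/d who experience a clinical complete response". Section 13.2.1 repeats the restriction to that dose: "treated with IL-2 combined with hydroxychloroquine at 600mg/d who experience a clinical complete response".

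For this objective Section 13.4 says that, barring treatment-limiting toxicity and early closure, "there will be 39 patients available for this objective". It then gives the precision: "A 95% exact binomial confidence interval on 5 responses out of 39 patients", described as the count expected if HCQ doubles a historic complete response (CR) rate of about 8%, "would have width equal to 0.27 (0.07,0.34"). For overall survival it assumes a 16-month median, 15 months of accrual and 15 more of observation; "then the expected width of the 95% confidence interval for median survival is 12.8 months".

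The patient numbers appear in four other places:

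- Section 2.18: the first five patients received 600 mg. "Out of the 13 patients treated with combination HCQ/IL-2 therapy using 1200 mg of Hydroxychloroquine", two had pronounced hypotension and tachycardia. The consequence is that "we are accruing another 21 patients to assess response in addition to the first five patients at the lower 600mg/d dose".
- Section 13.3.1: 21 additional patients at 600 mg/day under the revised protocol.
- Summary and Schema: 600 mg/d at all sites, with 21 given as the total group.
- Section 13.1: an accrual goal of 39, with 600 mg/day as the starting dose for everyone.

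**The concern.** The trial is designed for estimation. It has no hypothesis test and no power calculation for the primary endpoint, so the interval in Section 13.4 is the whole justification of its size. Two things in that sentence do not hold together. The interval does not belong to the data named beside it. And the denominator cannot be matched to the account of who received 600 mg/d unless 13 patients treated at 1200 mg are counted.

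The second matters more. If 39 stands as the denominator and is made up as Section 2.18 suggests, a third of it (13/39) was treated at a dose outside the stated objective. If 26 is the denominator, the plan promises more precision than it will deliver. As the text stands, a reader cannot tell which patients enter the primary estimate.

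**Working it through.** **1. The plan's own interval.** Inputs from Section 13.4: x = 5, n = 39, two-sided 95%, exact binomial. The Clopper-Pearson limits are

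- lower = Beta quantile(0.025; x, n − x + 1) = Beta quantile(0.025; 5, 35) = 0.0430
- upper = Beta quantile(0.975; x + 1, n − x) = Beta quantile(0.975; 6, 34) = 0.2743
- width = 0.231

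The printed (0.07, 0.34), width 0.27, is not reproduced. Other methods do not give it for 5/39 either: Wilson (0.056, 0.267), Agresti-Coull (0.051, 0.272), Jeffreys (0.051, 0.258), Wald (0.023, 0.233), mid-p (0.049, 0.262), 90% exact (0.052, 0.251), 98% exact (0.034, 0.303), 99% exact (0.029, 0.322). No other count in 39 gives it: 6/39 is (0.059, 0.305) and 7/39 is (0.075, 0.335). Among all x/n with n from 10 to 69, only 6/35 has an exact 95% interval that rounds to the printed limits: (0.066, 0.336), width 0.271.

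**2. The count of 5.** The text ties it to a doubled historic CR rate of about 8%. Expected responses in 39:

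- 2 × 8% = 16%: 39 × 0.16 = 6.2
- 2 × 8/95 = 16.8% (8/95 is the CR source for the monitoring prior in Section 13.3.2): 39 × 0.168 = 6.6
- 2 × 17/255 = 13.3% (Section 2.2, printed there as 7%): 39 × 0.133 = 5.2

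Only the third gives 5, and that rate is not about 8%.

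**3. The denominator.**

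| Place | 600 mg/d patients |
|---|---|
| 13.4 | 39 for this objective |
| 13.1 | 39 accrual goal, all starting at 600 mg/day |
| 2.18 | 5 treated + 21 to come = 26 (sum not printed); 13 others at 1200 mg |
| 13.3.1 | 21 additional |
| Summary and Schema | 21 as the total group |

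5 + 21 = 26, and 5 + 13 + 21 = 39.

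**4. Exact 95% intervals by n and rate.** The count is the expected number rounded to the nearest whole patient.

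| Doubled rate | n | Expected | Count | Interval | Width | Printed 0.27 minus width |
|---|---|---|---|---|---|---|
| 8/95 (16.8%) | 39 | 6.57 | 7 | (0.08, 0.34) | 0.26 | +0.01 |
| | 26 | 4.38 | 4 | (0.04, 0.35) | 0.31 | −0.04 |
| | 21 | 3.54 | 4 | (0.05, 0.42) | 0.36 | −0.09 |
| 8% (16%) | 39 | 6.24 | 6 | (0.06, 0.31) | 0.25 | +0.02 |
| | 26 | 4.16 | 4 | (0.04, 0.35) | 0.31 | −0.04 |
| | 21 | 3.36 | 3 | (0.03, 0.36) | 0.33 | −0.06 |
| 17/255 (13.3%) | 39 | 5.20 | 5 | (0.04, 0.27) | 0.23 | +0.04 |
| | 26 | 3.47 | 3 | (0.02, 0.30) | 0.28 | −0.01 |
| | 21 | 2.80 | 3 | (0.03, 0.36) | 0.33 | −0.06 |

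Averaging the width over the binomial distribution, so that rounding the count plays no part, gives 0.23 to 0.25 for n = 39, 0.28 to 0.31 for n = 26 and 0.31 to 0.34 for n = 21.

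**5. The survival width.** Assume exponential survival and uniform accrual. With λ = ln 2/16 = 0.0433 per month,

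P(event) = 1 − (e^(−15λ) − e^(−30λ))/(15λ) = 0.616.

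Expected events d = 39 × 0.616 = 24.0. Width = 2 × 1.96 × 16/√d = 12.8 months, which reproduces the plan. For n = 26, d = 16.0 and the width is 15.7 months.

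**The case against.** The strongest reply is that nothing downstream uses the printed interval. No test or stopping boundary depends on it, and Section 13.2.1 will compute the final interval from the observed data. If 39 is right, the printed width is slightly conservative; for 3/26 it is off by only 0.007. All of that is correct, and it is why the wrong interval by itself is only a correction to a stated figure. It does not settle who belongs in the primary estimate.

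It can also be said that 26 is never printed, and that Section 13.3.1 and Section 2.18 use 21 for new enrolment, not as a competing denominator. This stands. Only the Summary and Schema reads as if 21 were the total, so the substantive conflict is 26 against 39 and the lines for 21 have weak support. Section 13.4 also makes its 39 conditional on no treatment-limiting toxicity and no early closure, but that condition does not explain how 39 arises from 5 + 21.

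Three stronger readings are tempting and go beyond the text. A reader might infer that the sponsor intends to pool the 1200 mg patients into the primary estimate. The sum 5 + 13 + 21 fits, but the documents never state it, and Sections 1.1 and 13.2.1 point the other way. A reader might infer from 6/35 that the interval was carried over from a design with 35 patients; that is a guess from a numerical match. And a reader might take the historic rate as wholly open. In fact the printed figure of about 8% points to 8/95, and it is the count of 5 that does not follow from it.

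**Conclusion.** The point holds on both parts. The number of patients behind the 600 mg/d primary estimate is inconsistent, chiefly 39 in Sections 13.1 and 13.4 against a derived 26 from Section 2.18. The exact interval printed for 5/39 is wrong: (0.04, 0.27), width 0.23, against a stated (0.07, 0.34), width 0.27. This is the only precision statement for the primary endpoint, so it must be put right, with the weight on the denominator.

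The effect on the stated width is modest. The printed 0.27 is about 0.01 to 0.04 too wide for 39 patients and about 0.01 to 0.09 too narrow for 26 or 21. These ranges assume Clopper-Pearson limits, expected counts rounded to whole patients, and a doubled historic rate between 13.3% and 16.8%. The upper end, 0.09, belongs to n = 21 at doubled 8/95; for n = 26 the shortfall is at most about 0.04. The documents do not establish which denominator is intended, and this review does not choose one.

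**What to change.** 1. Reconcile the Summary and Schema and Sections 2.18, 13.1, 13.3.1 and 13.4 on how many patients at 600 mg/d form the primary analysis set. If the number is 26 (or 21), keep the 1200 mg patients out of the primary estimate, as Section 13.2.1 implies, and label any estimate pooled over doses a sensitivity analysis.
2. Name the historic CR rate. The printed figure of about 8% points to 8/95; if 17/255 is meant, change it to about 7%.
3. Replace the interval sentence in Section 13.4 with the line of the table in step 4 of the working that matches the chosen n and rate. At doubled 8/95 these are 7/39, (0.08, 0.34), width 0.26; 4/26, (0.04, 0.35), width 0.31; or 4/21, (0.05, 0.42), width 0.36.
4. If n is not 39, restate the survival width: 15.7 months for 26 in place of 12.8.

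Two short clarifications could be made in the same edit: which patients Table 8 counts, since its rows run to 36, and whether a single 15-month accrual period still applies when Section 2.18 reports 5 + 13 = 18 patients already treated.

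The cost is alignment of five places in the text and one recomputed sentence, plus the survival width if n changes. If 26 or 21 is confirmed, no extra patients are needed, and the stated width rises to between 0.28 and 0.36. If 39 at 600 mg/d is confirmed, that is 39 − 26 = 13 more patients at that dose than Section 2.18 describes, and the stated width falls to between 0.23 and 0.26.
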